8.2.3.7 Duration of Remission (DoR)

DoR is defined as time from date of first response in responders (CR/CRi by investigator assessment) to date of PFS event (see definition of PFS above). Responders without PFS event will be censored at the last valid disease assessment including follow-up disease assessment.

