7.3.6. Administration status and response evaluation for each cycle of BESPONSA®

Record the following with regard to administrative status and response evaluation for each cycle. Record administrative status of all cycle until the last administration dose. Refer to LPD for posology and method of administration.

- Administration date

- Body surface area
- Administration dose
- Pre-medication: If 'conducted', record the detailed information in '4.Concomitant medication' clause in CRF.
- Response evaluation after each cycle: Record the evaluation date and response. Select one among 'CR', 'CRI', 'refractory disease', 'progressive disease', or 'relapsed disease'. Response Criteria is defined according to *NCCN Guideline Version 2.2016 Acute Lymphoblastic Leukemia*⁹. Refer to Appendix 1 for detailed Response Criteria. If response evaluation is not done, check 'undone' and leave the evaluation date blank.

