APPENDIX 1. RESPONSE CRITERIA

APPENDIX 1. RESPONSE CRITERIA

Response Criteria is defined according to 'NCCN Guideline Version 2.2016 Acute Lymphoblastic Leukemia⁹'.

The below outcome definitions will be used for reporting of response assessments.

Response Criteria for Blood and Bone Marrow:

- Complete response (CR)
 - No circulating blasts or extramedullary disease
 - No lymphadenopathy, splenomegaly, skin/gum infiltration/testicular mass/central nervous system involvement
 - Trilineage hematopoiesis and < 5% blasts
 - Absolute neutrophil count (ANC) > 1000/microL
 - Platelets > 100,000/microL
 - No recurrence for 4 weeks
- CR with incomplete blood count recovery (CRi)
 - Meets all criteria for CR except platelet count and/or ANC
- Refractory disease
 - Failure to achieve CR at the end of induction
- Progressive disease
 - Increase of at least 25% in the absolute number of circulating or bone marrow blasts or development of extramedullary disease
- Relapsed disease
 - Reappearance of blasts in the blood or bone marrow (>5%) or in any extramedullary site after a CR

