8.2.3.5 Effectiveness(Best overall response)

In order to identify effectiveness (best overall response) of BESPONSA®, the 'effectiveness' is judged as follows based on the best overall response during evaluation and summarized by the number of subjects(n), percentage(%) and 95% confidence interval of percentage.

- Effective: CR, CRI
- Ineffective: Refractory disease, Progressive disease, Relapsed disease

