8.2.3.5 Progression-free survival (PFS)

PFS is defined as time from date of enrollment to earliest date of the following events:

PFIZER CONFIDENTIAL

CT24-WI-GL03-RF02 3.0 *Non-Interventional Statistical Analysis Plan for Primary Data Collection Study*
Page 14 of 17

- Death
- Refractory disease
- Progressive disease
- Relapsed disease

Subjects without a PFS event at time of analysis will be censored at the last valid disease assessment. In addition, subjects with documentation of an event after an unacceptably long interval (>28 weeks if there was post-baseline disease assessment, or >12 weeks if there was no post-baseline assessment) since the previous disease assessment will be censored at the time of the previous assessment (date of enrollment if no post-baseline assessment). Post-study treatment follow-up disease assessments will be included.

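### Duration of remission ends at a PFS event that need not follow the response, so a responder with an earlier refractory or progressive entry gets a negative duration

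*SAP*

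**What the plan says.** Several section numbers in this part of the SAP are used twice, so headings are given as well.

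- **SAP 8.2.3.7 (Duration of Remission).** DoR is "time from date of first response in responders (CR/CRi by investigator assessment) to date of PFS event (see definition of PFS above". Censoring is given in one sentence: "Responders without PFS event will be censored at the last valid disease assessment including follow-up disease assessment".
- **SAP 8.2.3.5 (Progression-free survival).** "PFS is defined as time from date of enrollment to earliest date of the following events"; the list is death, refractory, progressive and relapsed disease. An event recorded after a long gap is set aside, and the subject is censored at the previous assessment. The gap is ">28 weeks if there was post-baseline disease assessment, or >12 weeks if there was no post-baseline assessment) since the previous disease assessment".
- **Protocol 7.3.6.** After each cycle the site is told: "Select one among 'CR', 'CRI', 'refractory disease', 'progressive disease', or 'relapsed disease". The only alternative is no evaluation: "If response evaluation is not done, check 'undone' and leave the evaluation date blank".
- **Protocol Appendix 1.** Refractory disease is "Failure to achieve CR at the end of induction". Relapsed disease presupposes an earlier CR.
- **SAP 8.2.3.5 (Best overall response).** Effectiveness is "judged as follows based on the best overall response during evaluation", with CR and CRi counted as effective.
- **SAP 9, Section II.** DoR appears in the publication output as Figure 3 only.

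**The concern.** DoR takes its end date from the PFS definition, and PFS looks for the earliest event since enrollment. For a responder, that event can precede the response. The form makes this possible because each of its five categories is either a response or a PFS event. A patient evaluated after cycle 1 who has not reached CR or CRi must be given an event category, even if remission follows at a later cycle.

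Such a patient's remission would end before it began. The real end of remission, such as a later relapse, would not enter the analysis because the PFS event date is already fixed. The SAP does not say how the value is handled, so whoever programs the figure would have to drop it, truncate it or redefine it after seeing the data. These choices can lead to different DoR curves.

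**Working it through.** The plan states no DoR, event count or response rate, so there is no figure to reproduce. The check applies the written rule to example patients.

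**Inputs from the documents**
- DoR start and end, and its censoring sentence: SAP 8.2.3.7 (Duration of Remission).
- Event list, earliest-date rule and long-gap rule: SAP 8.2.3.5 (PFS).
- Five response categories after each cycle: Protocol 7.3.6.
- Up to six cycles: SAP 8.2.1.5.

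**Assumptions (not in the documents)**
- Enrollment is at day 0 and evaluations fall every s = 21 or 28 days.
- Evaluation 1 is refractory or progressive, the first CR is at evaluation r, and relapse is at evaluation 6.

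**Step 1: PFS date as written.** The earliest event is evaluation 1, so PFS = 1 × s = 21 or 28 days.

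**Step 2: DoR as written.** PFS date minus response date = s − r·s = (1 − r)·s.

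**Step 3: DoR with the event required to follow the response.** 6s − r·s = (6 − r)·s.

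| First CR at evaluation r | As written, s = 21 / 28 | Event after response, s = 21 / 28 |
|---|---|---|
| 2 | −21 / −28 days | +84 / +112 days |
| 3 | −42 / −56 days | +63 / +84 days |
| 4 | −63 / −84 days | +42 / +56 days |

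**Step 4: a responder with no later event.** Refractory at evaluation 1, CRi at 2, CR at 3, nothing afterwards. As written, DoR is (1 − 2)·s = −21 or −28 days and counts as an event. With the order required, it is censored at (3 − 2)·s = +21 or +28 days.

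**Step 5: a control patient.** CR at evaluation 1, relapse at evaluation 6. DoR is (6 − 1)·s = 105 or 140 days under both rules. Responders in CR or CRi at their first evaluation, or whose earlier cycles were not evaluated, are unaffected.

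**Step 6: does another rule repair it?**
- The DoR censoring sentence covers only responders without a PFS event. This patient has one.
- If enrollment precedes all evaluations, the earliest pre-response event is the first post-baseline assessment, because any evaluated status before CR or CRi is itself an event category. Only the 12-week limb of the long-gap rule can then apply: 12 × 7 = 84 days. It sets aside a first event entry dated after day 84. Evaluations 1 to 4 at 21-day spacing (4 × 21 = 84) and 1 to 3 at 28-day spacing (3 × 28 = 84) stay events. The first evaluation done would have to be the fifth (day 105) or the fourth (day 112) for the rule to act.
- Appendix 1 does not bar a CR or CRi after a refractory or progressive entry.

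**The case against.** The best defence is that a duration from one date to another presupposes their order, so any programmer would read the event as following the response, and a negative value would be noticed. That is probably what the authors intended. But the DoR clause refers expressly to the PFS definition, and no passage in either document orders the two dates. Noticing a negative value also does not settle what replaces it.

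The second defence is that the trigger is narrow. By Appendix 1, refractory disease belongs to the end of induction, and relapse cannot precede a first response unless the CR came from earlier therapy. This stands as a limit on frequency. What remains is progression followed by CR or CRi, a refractory entry at the end of induction followed by a later response, and entries made outside the criteria.

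Third, the day-84 boundary holds only if enrollment precedes every evaluation. Protocol 9.2 provides for patients already exposed when they sign the data privacy statement, so the condition may fail for some.

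A reader might go further and infer that the PFS definition is also wrong, or that its disagreement with best overall response is an error. The documents do not support that. The SAP lists refractory disease as a PFS event and dates it by the earliest occurrence. Cancelling that event because the patient later responds would make event status depend on future data. PFS and best overall response measure different things and may differ for one patient.

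**Conclusion.** The concern holds for DoR. As written, the rule gives an impossible value for any responder with a refractory or progressive entry before the first CR or CRi, unless the long-gap rule removes that entry. In the worked patient with CR at evaluation 2, the difference is -21 against +84 days, or -28 against +112 days. These figures rest on the assumed spacing, enrollment at day 0 and relapse at evaluation 6; the negative sign requires only that the event precede the response.

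A reader might infer that a sizeable share of the 100 patients is affected. The documents give neither a response rate nor the frequency of response after such an entry, so no count can be derived, and it may be zero. Nor does the error reach the MFDS tables or overall survival. It concerns one publication figure in a descriptive study with no formal hypothesis (SAP 4). It should be fixed because the stated rule fails and the remedy is simple.

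**What to change.** In SAP 8.2.3.7 (Duration of Remission):

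1. Define DoR as the time from first CR or CRi to the first relapsed, progressive or refractory entry, or death, dated after that response.
2. Censor responders with no such later event at their last valid disease assessment, follow-up assessments included.
3. State that the long-gap rule applies to DoR using assessments on or after the response.

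The PFS definition need not change. Optionally, add a sentence there confirming that a refractory or progressive entry before the response remains a PFS event, so that PFS and best overall response can differ for such a patient.

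The cost is SAP wording and derivation code. The evaluation dates and response categories needed are already collected for each cycle.

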8.2.4 Non-safety population Analyses

The following adverse events from non-safety population shall be summarized by SOC and PT using the number of subjects(n), percentage(%), number of events and 95% confidence interval of percentage.

- AE·ADR
- Serious AE·ADR
- Unexpected AE·ADR
- Unexpected serious AE·ADR

8.2.5 Non-PMS Analyses

Adverse events which were reported spontaneously or collected from other clinical studies or articles shall be summarized using the number of events by PT of MedDRA version 22.1(or the latest version at the time of analysis).

- AE·ADR
- Serious AE·ADR
- Unexpected AE·ADR

PFIZER CONFIDENTIAL

CT24-WI-GL03-RF02 3.0 *Non-Interventional Statistical Analysis Plan for
Primary Data Collection Study*
Page 15 of 17

- Unexpected serious AE·ADR

9. LIST OF TABLES AND TABLE SHELLS

Section I. Analysis for MFDS

Table 1. Patient disposition

Table 2. Demographics and underlying disease information

Table 3. Previous systemic therapy

Table 4. Previous hematopoietic cell transplant

Table 5. Past disease

Table 6. Present disease

Table 7. Veno-occlusive liver disease/Sinusoidal obstruction syndrome(VOD/SOS)

Table 8. Hepatic disorder

Table 9. Renal disorder

Table 10. Allergic history

Table 11. Concomitant medication

Table 12. Administration status of BESPONSA® – Total

Table 13. Summary of Adverse Events

Table 14. Adverse event – AE·ADR

Table 15. Adverse event – Serious AE·ADR

Table 16. Adverse event – Unexpected AE·ADR

Table 17. Adverse event – Unexpected serious AE·ADR

Table 18. Characteristics of adverse events

Table 19. Adverse events by Severity by SOC/PT

Table 20. Adverse events by Action taken by SOC/PT

Table 21. Adverse events by SAE categories by SOC/PT

Table 22. Adverse events by Outcome by SOC/PT

Table 23. Adverse events by Causality to the study drug by SOC/PT

Table 24. Adverse events by Other causality by SOC/PT

Table 25. Categorical factor analysis for adverse events

Table 26. Continuous factor analysis for adverse events

Table 27. Multiple logistic regression for adverse event for the final re-examination

Table 28. Adverse event in elderly(≥65 years) group

Table 29. Adverse event in hepatic disorder group

Table 30. Adverse event in renal disorder group

Table 31. Response evaluations

Table 32. Last effectiveness

Table 33. Categorical factor analysis for last effectiveness

Table 34. Continuous factor analysis for last effectiveness

Table 35. Multiple logistic regression for last effectiveness for the final re-examination

Table 36. Effectiveness(Best overall response)

Table 37. Categorical factor analysis for effectiveness(best overall response)

Table 38. Continuous factor analysis for effectiveness(best overall response)

Table 39. Multiple logistic regression for effectiveness(best overall response) for the final re-examination

Table 40. Non-safety population – AE·ADR

Table 41. Non-safety population – Serious AE·ADR

Table 42. Non-safety population – Unexpected AE·ADR

Table 43. Non-safety population – Unexpected serious AE·ADR

Table 44. Non-PMS Analyses – AE·ADR

Table 45. Non-PMS Analyses – Serious AE·ADR

Table 46. Non-PMS Analyses – Unexpected AE·ADR

Table 47. Non-PMS Analyses – Unexpected serious AE·ADR

Section II. Analysis for publication

Table 1. Progression-free survival(PFS)

Table 2. Overall survival(OS)

Figure 1. Progression-free survival(PFS)

Figure 2. Overall survival(OS)

Figure 3. Duration of remission(DoR)

